Protocol title: The MLN9708 for the prophylaxis of chronic graft-versus-host disease in patient undergoing allogeneic transplantation.

Document date: 03-13-18

NCT number: NCT02250300

The MLN9708 for the prophylaxis of chronic graft-versus-host disease in patient undergoing allogeneic transplantation.

Principal Investigator: [name]
Associate Professor of Medicine,
Division of Hematology and Oncology
Froedtert Hospital and the Medical College of Wisconsin
[name]
[name]

Protocol Team: [name], MRCP, MS
[name]
[name]
[name]
[name]
[name]
[name]
[name]
[name]
[name]
[name]
[name]
[name]

Statistician: [name], MS
Biostatistician II
Division of Biostatistics
Institute for Health and Society
[contact]

Study Coordinator:
For Medical College of Wisconsin:
[name]
Froedtert Hospital and the Medical College of Wisconsin
Cancer Center Clinical Trials Office
[name]
[name]
[contact]-[**[name]**](tel:[name])
[contact]
Email: [**[contact]**](mailto:[contact])

Pharmacist

For Medical College of Wisconsin:

[name], Pharm D.

Froedtert Hospital

Inpatient Pharmacy

Attn: [name]

[name]

[name]

CLINICAL STUDY PROTOCOL

Protocol Number = IISR-2013-M100104; Grant Number: X16034
MLN9708 for the prophylaxis of chronic graft-versus-host disease in patient undergoing allogeneic transplantation.

Indication: Chronic graft-versus-host disease prophylaxis
Phase: Phase I/II

Protocol History

Original	23 August 2013
Amendment 1	04 November 2014
Amendment 2	25 June 2015
Amendment 3	15 March 2017
Amendment 4	14 September 2017
Amendment 5	13 March 2018

This is an investigator-initiated study. The principal investigator [name] (who may also be referred to as the sponsor-investigator), is conducting the study and acting as the sponsor. Therefore, the legal/ethical obligations of the principal investigator include both those of a sponsor and those of an investigator.

PROTOCOL SUMMARY

Study Title: MLN9708 for the prophylaxis of chronic graft-versus-host disease.
Phase: Phase I/II
Number of Patients: 6 patients were enrolled in phase I portion. No DLTs were seen. In the phase II portion a total of 52 patients (25 sibling and 27 unrelated donor transplantation) will be enrolled. Total accrual = 58 patients.
Study Objectives
Primary Objectives:
Phase I Primary Objectives:

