- Tapering of any concomitant acute GVHD prophylaxis will be per institutional guidelines, however in absence of acute GVHD, renal insufficiency and disease relapse/progression it is recommended that taper **SHOULD NOT** commence before day +100. The recommended goal of tapering is the complete discontinuation of immunosuppressive medications by day +180.

Excluded Concomitant Medications and Procedures

The following medications and procedures are prohibited during the study:

Systemic treatment with any of the following metabolizing enzyme inhibitors is not permitted during this study. A DDI with a strong inhibitor would increase MLN2238 exposure.

- Concomitant administration of strong inhibitors of CYP1A2 (fluvoxamine, enoxacin, ciprofloxacin) and strong inhibitors of CYP3A (clarithromycin, telithromycin, itraconazole, voriconazole, ketoconazole, nefazodone, and posaconazole).

Systemic treatment with any of the following metabolizing enzyme inducers should be avoided unless there is no appropriate alternative medication for the patient to use. A DDI with a strong inducer would decrease MLN2238 exposure.

- Strong CYP3A inducers (rifampin, rifapentine, rifabutin, carbamazepine, phenytoin and phenobarbital).
- The dietary supplements St. John's wort and Ginkgo biloba are not permitted.
- Antibiotic prophylaxis will be given according to institutional guidelines. Herpes zoster prophylaxis per institutional guidelines will be required during prophylaxis with MLN9708.
- Patients missing a single dose of MLN9708 (due to decreased oral intake secondary to severe nausea, vomiting, mucositis etc.) should be discussed with study PI. Patients missing >1 dose will need to be replaced. In case MLN9708 therapy is interrupted, the time interval should be recorded.
- Toxicity will be evaluated according to CTCAE v4.0.
- Progression free survival (PFS) and overall survival (OS) following transplantation will be recorded.

Dose modification

- Patients experiencing a grade 3-4 hematological or non-hematological toxicity (as specified in CTCAE v4.0) thought to be related to MLN9708 will be removed from the study permanently (except the exceptions allowed in Table 3). No dose modifications are permitted.

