concluding the new treatment is promising, will be 0.80 (statistical power) when the true but unknown rate of developing chronic GVHD is 30% or 0.04 (type I error) when the true rate is 55% in related donor transplantation (Cohort A [matched sibling donor transplantation] with a sample size of 25). Similarly, the probability of concluding the new treatment is promising, will be 0.81 (statistical power) when the true but unknown rate of developing chronic GVHD is 40% or 0.05 (type I error) when the true rate is 65% in unrelated transplantation (Cohort B [unrelated donor transplantation] with a sample size of 26). The efficacy endpoint is chronic GVHD-free at 1 year and there will be no interim analysis on efficacy for this multi-center study. In the final analysis in Cohort A, if 10 or more of 25 patients have chronic GVHD, we will conclude the new treatment is ineffective in Cohort A; for Cohort B, if 13 or more of 26 patients have chronic GVHD, we will conclude the new treatment is ineffective in Cohort B.

Demographic and baseline laboratory results will be summarized using descriptive statistics, including means with standard deviations, or medians with ranges, histograms and box-plot. The chronic GVHD rate at 1-year and its 95% CI will be calculated by cumulative incidence method, while accounting for competing events. Progression-free survival and overall survival will be estimated using the Kaplan-Meier method.

Cumulative incidence of acute and chronic GVHD, disease relapse and non-relapse mortality will be calculated by accounting for competing events. Competing events for acute GVHD disease are relapse or death without acute GVHD, while those for chronic GVHD are relapse or death without chronic GVHD. Disease relapse and non-relapse mortality are competing events for each other. Toxicity will be reported by type, frequency and severity. Worst toxicity grades per patient will be tabulated for selected adverse events and laboratory measurements. Patients replaced on the protocol (as specified in the Dose Modification Section) will remain evaluable for safety and toxicity assessment.

Safety/Stopping Rules:

For the phase II portion of the study we propose to accrue 51 patients over 24–30 months, which will enroll about 12 patients every 6 month time period. We plan to

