monitor and evaluate short term adverse events at each additional 12 patients who have been enrolled in the study. The expected 100 day post-transplant immunologic graft rejection (defined as less than 5% donor myeloid cells) rate is approximately 2.5% (in absence of relapsed disease) and the enrollment will be put on hold if more than 5% graft rejection rate is seen. For the development of grade 3-4 adverse events deemed to be related to MLN9708, the true rate is 5% and enrollment will be on hold if more than 10% adverse events are observed. The stopping boundaries for graft rejection and development of grade 3-4 adverse events are shown in Table below. In the case of a safety event suspending study, a prompt cumulative examination of all data and circumstances of these events will be conducted by the Medical College of Wisconsin DSMC to determine whether study should be resumed, whether the protocol will be revised or whether the study will be discontinued permanently.

Table. Stopping boundary for adverse events.

Number of patients enrolled	Stopping boundary for immunologic graft-rejection	Stopping boundary for developing grade 3-4 adverse events related to MLN9708
12	≥ 3	≥ 3
24	≥ 3	≥ 4
36	≥ 4	≥ 6
48	≥ 4	≥ 6
51	≥ 5	≥ 7

Accrual Estimate: 6-12 patients will be enrolled in the phase I part of the protocol. In the phase II portion a total of 52 patients (25 sibling and 27 unrelated donor transplantation) will be enrolled, with 1-3 per month. Total estimated accrual = 58 patients.

Accrual Period : Approximately 24-30 months

Follow-Up Period : Two years to evaluate incidence of acute and chronic GVHD and relapse pattern, and five years for survival outcomes.

10. Adverse Event Reporting Requirements

11. Definitions

The following are definitions of adverse events as defined by 21CFR312.32.

Types of Adverse Events

Adverse Event (AE) means any untoward medical occurrence associated with the use of a drug in humans, whether or not consider drug related. An AE can therefore be any unfavorable and unintended sign (including an abnormal laboratory finding), symptom, or disease temporally associated with the use of a medicinal (investigational) product whether or not it is related to the medicinal product. This includes any newly occurring event, or a previous condition that has increased in severity or frequency since the administration of study drug.

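### Cohort B is sized and judged at 26 patients but enrolled at 27, and no decision rule is given for 27

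*Combined protocol and SAP*

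**What the plan says.** Section 9 (Statistical Considerations) tests a null 1-year chronic GVHD rate of 65% against 40% in Cohort B by the exact binomial. The stated type I error is 0.05 and power 0.81, "in unrelated transplantation (Cohort B [unrelated donor transplantation] with a sample size of 26". The decision rule uses the same number: "for Cohort B, if 13 or more of 26 patients have chronic GVHD, we will conclude the new treatment is ineffective in Cohort B". Under Safety/Stopping Rules the phase II total follows from it: "For the phase II portion of the study we propose to accrue 51 patients", and the last row of the stopping table is also 51.

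The Accrual Estimate at the end of the same section gives a different number: "In the phase II portion a total of 52 patients (25 sibling and 27 unrelated donor transplantation) will be enrolled, with 1-3 per month". The Protocol Summary repeats 25 and 27 and adds the six phase I patients: "Total accrual = 58 patients".

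Cohort A is 25 wherever it appears, and its rule is "if 10 or more of 25 patients have chronic GVHD, we will conclude the new treatment is ineffective in Cohort A". Section 5 (Treatment Plan) says "Patients missing >1 dose will need to be replaced". Section 9 says only that replaced patients stay evaluable for safety and toxicity. It does not say whether they count for efficacy.

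**The concern.** Both Cohort B sizes stand in current text, and Section 9 contains both. The rule decides whether the drug is called ineffective in that cohort, yet it is written for one patient fewer than the plan says it will enrol. With 27 outcomes in hand, someone would have to choose a cut-off or leave a patient out. The trial is single-arm and open-label, so a choice made after the outcomes are known could be driven by them. The same question of who is counted arises if patients are replaced, because no efficacy analysis set is defined.

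**Working it through.** **Inputs.** Section 9: Cohort B null 0.65 and alternative 0.40, n = 26, promising if 12 or fewer events. Cohort A null 0.55 and alternative 0.30, n = 25, promising if 9 or fewer. Enrolment of 27 is from the Protocol Summary and the Accrual Estimate.

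**Totals.** 25 + 26 = 51 (safety section, last stopping row). 25 + 27 = 52 (Summary, Accrual Estimate). 6 + 52 = 58 (Summary). With 26 the overall total would be 6 + 51 = 57.

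**Formula.** With X the number of patients with chronic GVHD, P(promising) = P(X ≤ c | n, p) = Σ C(n,k) p^k (1 − p)^(n−k), summed over k = 0 to c. This is the type I error at the null rate and the power at the alternative.

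**The plan's own rules**

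| Rule | Type I error, exact | Stated | Power, exact | Stated |
|---|---|---|---|---|
| A: n = 25, ≤ 9 | 0.044 | 0.04 | 0.811 | 0.80 |
| B: n = 26, ≤ 12 | 0.038 | 0.05 | 0.801 | 0.81 |

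Both powers reproduce to within about 0.01. The 0.05 for Cohort B fits only as a nominal ceiling.

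**Cohort B at 27**

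| Rule | Type I error | Power |
|---|---|---|
| n = 27, ≤ 12 | 0.023 | 0.750 |
| n = 27, ≤ 13 | 0.054 | 0.855 |

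Both quantities rise with the cut-off. Anything below 12 has power under 0.750 and anything above 13 has error over 0.054, so no cut-off at 27 meets both 0.05 and 0.80.

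**Which outcome is ambiguous if all 27 are analysed?** The rule's boundary is 13/26 = 50.0%.
- 12 or fewer events: promising as a count and as a proportion.
- 14 or more: ineffective on both (14/27 = 51.9%).
- 13: ineffective as a count, not as a proportion (13/27 = 48.1%).

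P(X = 13 | 27, p) = C(27,13) p^13 (1 − p)^14 = 0.1055 at p = 0.40 and 0.0307 at p = 0.65.

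**If 26 of the 27 are analysed and 13 of the 27 had events.** Leaving out a patient with chronic GVHD gives 12/26, promising. Leaving out one without gives 13/26, ineffective. Nothing in the plan says who is left out.

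**The case against.** The best defence is that 26 is plainly the analysis size. The power statement, the decision rule, the phase II total of 51 and the last stopping row all use it, and 27 appears only in enrolment statements. On that view the 27th patient is a spare. This is plausible, but no text calls the extra patient an allowance, and 51 is itself given as the number to accrue.

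A second defence is that the primary objective is to estimate a cumulative incidence with a 95% confidence interval, which needs no fixed 26 or 27. That is correct for the estimate. It does not rescue the rule, which attaches a conclusion of ineffectiveness to a count out of 26.

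Three stronger readings are tempting, and the documents support none of them.
- A reader might infer that Cohort A has the same contradiction. It does not: its size is 25 throughout. Keeping replaced patients evaluable for safety and toxicity suggests that they leave the efficacy count, and then its rule applies as written. What stands is that this is not stated.
- A reader might infer that the authors really designed for 27, since 0.054 rounds to 0.05. But that rule has power 0.855, not 0.81, and the other cut-off at 27 gives 0.023 and 0.750. Neither matches the stated pair.
- A reader might infer from the stated 0.05 and 0.81 that the Cohort B design fails. It does not: at 26 the exact error is lower than stated and power is still 0.80. These are matters of rounding and labelling.

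**Conclusion.** The point holds for Cohort B. Two sizes stand in current text, the only rule is written for 26, and 27 cannot simply take its place because no cut-off there keeps error at or below 0.05 with power at or above 0.80. The effect on the conclusion is narrow: only 13 events among 27 analysed patients is read two ways, with probability 0.11 at a 40% rate and 0.03 at 65%. Those figures assume that exactly 27 patients contribute a 1-year outcome and that outcomes are independent with a common rate. The documents do not allow the chance of 27 contributing to be calculated. If exactly 26 contribute and no patient has been left out, the written rule applies and nothing is lost. For Cohort A the point is only a conditional clarification of who counts.

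**What to change.** Make these changes before 1-year outcomes are reviewed.

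1. Keep 26 as the Cohort B efficacy analysis size, promising if 12 or fewer events. Restate its exact type I error as 0.038 and power as 0.80, and Cohort A's power as 0.81.
2. Reconcile the totals in one of two ways. Either correct 27/52/58 to 26/51/57, or label 27/52/58 as enrolled and 26/51 as evaluable. In the second case add a stopping-table row for 52 if 52 are enrolled, and pre-state an outcome-blind rule for who is analysed, such as the first 26 patients in order of enrolment who meet the efficacy-set definition.
3. Alongside this, say whether three groups count in the 25 and the 26: patients replaced for missing more than one dose, patients removed for toxicity, and patients who relapse or die before 1 year without chronic GVHD.

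The cost is protocol wording, with no added patients or visits. The stated Cohort B power falls from 0.81 to 0.80.

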- If a patient experiences a Grade 3 or 4 non-drug-related renal function impairment or hepatic function impairment, MLN9708, can be held until recovery to Grade 1 or baseline (up to a maximum of 14 days). Upon recovery of the toxicity to a level allowing continuation of therapy, a dose reduction is not necessary.

Duration of therapy

MLN9708 will be continued until any one of the following criteria is met:

- Patient finishes four doses of MLN9708.
- Patient develops grade III-IV acute GVHD.
- Patient develops severe chronic GVHD.
- Patient develops any grade 3-4 toxicity related to MLN9708 use.

Data Safety Monitoring Plan

The Medical College of Wisconsin (MCW) Cancer Center (CC) Data Safety Monitoring Committee (DSMC) is responsible for monitoring data quality and subject safety for all cancer center investigator initiated clinical trials. A six to eight member Data and Safety Monitoring Committee will complete a review of protocol-specific data safety monitoring reports, to provide recommendations on trial continuation, suspension or termination.

A summary of the MCW CC DSMC activities are as follows:

- Review the clinical trial for data integrity and safety
- Review all unexpected grade 3, and all grade 4, and 5 adverse events, as well as any others requiring expedited reporting as defined in this protocol. (Grades 4 & 5 events must be reported to the DSMC within 5 calendar days of study staff's knowledge.)
- Review all DSMC reports
- Submit a summary of any recommendations related to study conduct
- Terminate the study if deemed unsafe for patients

A copy of the MCW CC Data and Safety Monitoring Plan and membership roster will be maintained in the study research file and updated as membership changes. The committee will

review reports from the study PI twice annually (or more frequently if needed) and provide recommendations on trial continuation, suspension or termination as necessary.

Any available DSMC letters will be submitted to the IRB of record as required.

6. Measurement of Effect:

Follow up schedule:

The schedule for follow up on the study is shown in the table below.

Study Visit	Approximate target Day Post-Transplant
1	60 days
2	67 days
3	74 days
4	81 days
5	90-100 days
6	180 days
7	365 days
8	2 years

Patients will be followed for survival, relapse and cause of death for 5 years post transplantation.

Phase I patients will be seen weekly for toxicity assessment during the DLT period.

GVHD Assessment:

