All unexpected grade 3, and all grade 4, and 5 adverse events, as well as any others requiring expedited reporting as defined in this protocol, will be reported to the MCW Cancer Center DSMC. (Grades 4 & 5 events must be reported to the DSMC within 5 calendar days of study staff's knowledge). If the Grade 3-5 event is determined to be an unanticipated problem, the event will be forwarded to the MCW IRB for review as required by their policy. Unexpected adverse events, regardless of severity, will be reported to the MCW Cancer Center DSMC and reviewed on a quarterly basis.

Expected Adverse Events

Expected adverse events that are being captured on the study toxicity form will be reported at the time of the form's scheduled due date.

All MCW Cancer Center DSMC reports and recommendations will be submitted to the IRB for their review.

Procedures for Reporting AESIs

AEs may be spontaneously reported by the patient and/or in response to an open question from study personnel or revealed by observation, physical examination, or other diagnostic procedures. Any clinically relevant deterioration in laboratory assessments or other clinical finding is considered an AE. When possible, signs and symptoms indicating a common underlying pathology should be noted as one comprehensive event. For non-serious AEs (including AESIs), the investigator must determine both the intensity of the event and the relationship of the event to study drug administration.

AESIs must be reported to Millennium on a quarterly basis.

Procedures for Reporting Drug Exposure during Pregnancy and Birth Events

If a woman becomes pregnant or suspects that she is pregnant while participating in this study, she must inform the investigator immediately and permanently discontinue study drug. The sponsor-investigator must immediately fax a completed Pregnancy Form to the Millennium Department of Pharmacovigilance or designee (see Section Reporting of Adverse Events). The pregnancy must be followed for the final pregnancy outcome.

If a female partner of a male patient becomes pregnant during the male patient's participation in this study, the sponsor-investigator must also immediately fax a completed Pregnancy Form to the Millennium Department of Pharmacovigilance or designee (see Section Reporting of Adverse Events). Every effort should be made to follow the pregnancy for the final pregnancy outcome.

Suggested Pregnancy Reporting Form:

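### Section 9 tests the safety boundaries only at every 12th patient, so enrolment can continue after a hold has become certain; holding when the count is reached saves about 3 to 5 patients per hold without changing the chance of a hold

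*Combined protocol and SAP*

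**What the plan says.** Section 9, Safety/Stopping Rules, plans 51 phase II patients, "which will enroll about 12 patients every 6 month time period", and will "monitor and evaluate short term adverse events at each additional 12 patients who have been enrolled in the study". Two sentences give percentage triggers. For graft rejection, "the enrollment will be put on hold if more than 5% graft rejection rate is seen"; for toxicity, "the true rate is 5% and enrollment will be on hold if more than 10% adverse events are observed". Then "The stopping boundaries for graft rejection and development of grade 3-4 adverse events are shown in Table below". The table reads:

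| Enrolled | 12 | 24 | 36 | 48 | 51 |
|---|---|---|---|---|---|
| Graft rejection, hold at | 3 | 3 | 4 | 4 | 5 |
| Related grade 3-4 events, hold at | 3 | 4 | 6 | 6 | 7 |

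Rows are indexed by total enrolment, and Section 9 keeps replaced patients evaluable for safety, so the counts are cumulative. A hold is a pause while the data safety monitoring committee (DSMC) examines all data. It is not a final stop.

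Other oversight is in the Data Safety Monitoring Plan (Section 5) and in Section 11. The DSMC reviews reports twice a year, or more often if needed. Its tasks include "Review all unexpected grade 3, and all grade 4, and 5 adverse events", and the same sentence adds any other event that the protocol sends by an expedited route. Grade 4-5 events must reach it within 5 calendar days. Expected events on the toxicity form "will be reported at the time of the form's scheduled due date".

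**The concern.** The looks are about 6 months apart, except the last, which follows 3 patients after the fourth. Suppose the third related grade 3-4 event is confirmed at patient 5. The look at patient 12 must then call a hold, but as written the study goes on enrolling and dosing seven more patients first. Waiting does not improve the hold decision, because the count at a look meets the boundary exactly when it was reached by that look. What is at stake is exposure of patients after the protocol's own pausing criterion has in substance been met.

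**Working it through.** **Inputs.** Looks, boundaries and expected rates (5% related grade 3-4 toxicity, 2.5% rejection) are from Section 9. Accrual is about 2 per month (12 per 6 months; Section 9 also gives 1-3 per month). Assumptions: one yes/no outcome per patient, independent between patients, final when known, and true rates above the expected ones as shown.

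**The plan's own figures.** Section 9 states no error rate, hold probability or expected enrolment for the table, so there is nothing to reproduce exactly. All ten boundaries equal the smallest count whose binomial upper tail at the expected rate is at most about 0.032. For example, P(X ≥ 3 | 12, 5%) = 0.0196 and P(X ≥ 4 | 48, 2.5%) = 0.0318. That cutoff is inferred, not stated.

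**Method.** The count is followed patient by patient. In the block ending at look L with boundary b, let i be the patient at whom the count first reaches b. The look rule holds at L, an immediate rule holds at i, and L − i patients are enrolled in between.

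**First block by hand, toxicity rate p = 20%.** The third event falls on patient i with probability C(i−1, 2) p³ (1−p)^(i−3). Summing (12 − i) times this over i = 3 to 12 gives 1.510. The probability of a hold at patient 12 is P(X ≥ 3 | 12, 0.2) = 0.4417. The mean gap is 1.510 / 0.4417 = 3.42 patients.

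**All blocks, exact recursion.** Each unconditional mean is the hold probability times the conditional mean.

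| True rate | P(hold), either rule | Mean extra, given a hold | Mean extra, all trials |
|---|---|---|---|
| Toxicity 5% | 0.0575 | 3.19 | 0.18 |
| Toxicity 10% | 0.4071 | 3.65 | 1.49 |
| Toxicity 20% | 0.9503 | 4.08 | 3.88 |
| Toxicity 40% | 1.0000 | 5.32 | 5.32 |
| Rejection 2.5% | 0.0421 | 4.25 | 0.18 |
| Rejection 5% | 0.2445 | 4.44 | 1.09 |
| Rejection 10% | 0.7416 | 4.76 | 3.53 |
| Rejection 15% | 0.9495 | 4.98 | 4.73 |

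**Maximum gap.** In the first block the third event can come no earlier than patient 3, so 12 − 3 = 9. In a later block one event may be enough: the third rejection at patient 13 gives 24 − 13 = 11.

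**In time.** At 2 patients per month, 4 patients is about 2 months of accrual and 11 is about 5.5 months.

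**Reporting lag.** If each outcome becomes known only two or three patients later, the conditional means are about 3 to 4 for toxicity and 4 to 5 for rejection. The two rules still give the same hold probability.

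**Text against table.** One rejection in 12 is 8.3%, above the 5% in the text. Two toxicities in 12 is 16.7%, above the 10% in the text. The table requires 3 of each.

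**The case against.** Several points on the other side stand.

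- A reader might infer that expected grade 3 events, or a chimerism result below 5%, have no early route to the DSMC. The documents do not support that. Section 11 requires every serious event, expected or not, to go to the drug supplier within 4 calendar days, and the DSMC clause takes in other events that need expedited reporting, so serious expected grade 3 events may well reach it. Graft rejection is not among the drug effects that the protocol lists. If the brochure does not list it either, it is unexpected: reportable at grade 3 or above, and reviewed quarterly at any grade. What remains is that non-serious expected grade 3 events wait for the form, and that no channel is linked to the boundary counts.
- The figures given a hold can suggest a large routine excess. At the expected rates it averages about 0.2 patients. Three toxicities within five patients has probability 0.1% at a 5% rate and 5.8% at 20%.
- Counts can fall. Relatedness may be re-attributed, and rejection counts only in the absence of relapsed disease, so certainty of a hold presumes final attribution.
- Not every third event makes a hold certain. A third toxicity after patient 12 does not, because the row at 24 needs 4.
- Looks in blocks are a coherent design, the DSMC may meet more often, related grade 3-4 toxicity ends that patient's dosing (apart from the exceptions that Section 5 allows), and the extra patients still add data.

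None of this supplies a reason to wait for the look once the coming row's number has been confirmed.

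**Conclusion.** The point holds as a cheap safety improvement. It does not show that the boundaries are wrong or that monitoring between looks is absent. The look-only rule delays its own pause by about 3 to 5 patients on average when a hold occurs, roughly 2 months of accrual or a little more, and by at most 11 patients. Averaged over all trials the cost is negligible at the expected rates and grows if the true rates are higher.

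Higher rates are assumed here, not predicted. Table 1-4 of the protocol reports drug-related grade 3 or higher thrombocytopenia in 38% with weekly single-agent treatment. That was a myeloma population with dose levels up to 3.95 mg/m², and the six phase I patients here had no dose-limiting toxicity.

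The equality of hold probabilities rests on per-patient counting, attribution that is final when counted, and use of the table. Any check, at looks or between them, is ambiguous until the percentage sentences and the table agree.

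**What to change.** In Section 9, state that enrolment is held for DSMC review as soon as the cumulative number of patients with a table event reaches the boundary of the next scheduled row, judged by the number enrolled when the event is confirmed. Keep the table numbers and event definitions: related grade 3-4 events, and donor myeloid chimerism below 5% without relapse. In Section 11, have sites report each such event to the sponsor-investigator and the DSMC within the 5 calendar days already used for grade 4-5 events.

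In the same edit:
- reconcile the 5% and 10% sentences with the table;
- state that counting is per patient;
- reconcile the last row (51) with the 52 patients (25 + 27) in the protocol summary and Accrual Estimate.

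The cost is a running count and a few more expedited reports, mainly of non-serious expected grade 3 events. No new assessment is needed, and the probability of a hold under the table, true or false, stays the same.

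### Phase II safety boundaries are read at fixed enrolment counts with no follow-up condition, so each look rests on partly observed patients and a hold may come late

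*Combined protocol and SAP*

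**What the plan says.** All of this is in Section 9, Safety/Stopping Rules, unless stated otherwise.

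- **Trigger.** The trial will "monitor and evaluate short term adverse events at each additional 12 patients who have been enrolled in the study". The first column of the boundary table is "Number of patients enrolled", with rows at 12, 24, 36, 48 and 51.
- **Boundaries.** Immunologic graft rejection: 3, 3, 4, 4, 5 events. Related grade 3-4 adverse events: 3, 4, 6, 6, 7 events.
- **Endpoints.** Graft rejection is a 100-day quantity: "The expected 100 day post-transplant immunologic graft rejection" rate is put at about 2.5%. No observation window is given for the adverse-event boundary.
- **Text thresholds.** For graft rejection, "enrollment will be put on hold if more than 5% graft rejection rate is seen". For adverse events, "the true rate is 5% and enrollment will be on hold if more than 10% adverse events are observed".
- **Accrual.** "we propose to accrue 51 patients over 24–30 months, which will enroll about 12 patients every 6 month time period". The accrual estimate gives a range of 1-3 per month.
- **Timing of patients.** Section 4 places enrolment ideally at day +60 to +90. Section 5 gives phase II doses on days 1, 8, 15 and 22. The Section 7 calendar has no chimerism draw between screening and the day 90-100 visit.
- **Phase I contrast.** Section 5 sets a toxicity observation period ending 28 days after the last dose, and the last patient at a level must have completed it before escalation. Phase II has no counterpart.

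**The concern.** A look triggered by the 12th enrolment takes place when that patient has had at most a first dose, and when others are in mid-dosing or have not had the day-100 chimerism test. They enter the row count in full but have had only part of their time at risk. A boundary set for 12 fully observed patients is therefore harder to reach than it appears, most of all at the first look, where the recent patients are the largest share. As written, an event that appears a week after a look is not set against a boundary until the next 12 patients have been enrolled, about six months later at planned accrual. What is at stake is how soon an excess of related toxicity or graft rejection leads to a hold.

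**Working it through.** **1. Reproducing the table.** For each row take the smallest r with P(X ≥ r | n, p0) below a constant level, where X is binomial, n is the number enrolled, and p0 is 2.5% (graft rejection) or 5% (adverse events). The plan gives no level. Solving backwards, a level of about 0.032 (between 0.0318 and 0.0324) reproduces all ten boundaries; 0.03 and 0.04 do not. The table therefore matches a calculation in which every enrolled patient is fully observed.

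**2. Patients not fully observed at a look.** Count the patient who triggers the look plus (monthly rate ÷ 30.4) × window in days, with the first dose on the day of enrolment.

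- Dosing unfinished (day 1 to day 22 = 21 days): 1 + 2 × 21/30.4 = 2.4 at 2 per month; 1.7 to 3.1 at 1-3 per month.
- Day 100 not reached (100 − 90 = 10 to 100 − 60 = 40 days after enrolment): 1 + 2 × 10/30.4 = 1.7 to 1 + 2 × 40/30.4 = 3.6 at 2 per month.
- If the phase I period were borrowed (21 + 28 = 49 days): 1 + 2 × 49/30.4 = 4.2, most of them with part of the window already observed.

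**3. First look, if d patients contribute nothing.** With m = 12 − d and a true adverse-event rate of 20%:

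P(X ≥ 3) = 1 − [0.8^m + m(0.2)(0.8)^(m−1) + (m(m−1)/2)(0.2)²(0.8)^(m−2)]

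- d = 0: 1 − (0.0687 + 0.2062 + 0.2835) = 0.442
- d = 2: 1 − (0.1074 + 0.2684 + 0.3020) = 0.322
- d = 3: 1 − (0.1342 + 0.3020 + 0.3020) = 0.262

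**4. All looks.** Exact recursion over the five looks, with n − d patients observed at each:

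| Endpoint, assumed true rate | Look | d = 0 | d = 2 | d = 3 |
|---|---|---|---|---|
| Adverse events, 20% | first | 0.442 | 0.322 | 0.262 |
| | by 24 | 0.752 | 0.682 | 0.642 |
| | all | 0.950 | 0.934 | 0.924 |
| Adverse events, 10% | first | 0.111 | 0.070 | 0.053 |
| | all | 0.407 | 0.360 | 0.336 |
| Graft rejection, 10% | first | 0.111 | 0.070 | 0.053 |
| | all | 0.742 | 0.709 | 0.691 |

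**5. Allowing for partial follow-up.** Patients in mid-dosing can already have had an adverse event, so step 3 is a worst case for a given d. Simulating random (Poisson) accrual at 2 per month, with first dose at enrolment and a 20% rate, the first-look hold probability is about 0.34 if events are spread over the 21 dosing days and about 0.29 if spread over 49 days.

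**6. Patients enrolled by the time of a hold (or the end), 20% rate.** Current rule against rows kept open until their patients mature:

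- 2 per month, events over 21 days: 26.3 against 24.0, a difference of 2.3.
- 2 per month, events over 49 days: 27.7 against 24.2, a difference of 3.5.
- 3 per month, events over 49 days: 29.0 against 24.4, a difference of 4.6.

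At the assumed 5% rate, the chance of any hold at 2 per month is about 4-4.5% under the current rule and about 6% with open rows.

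**7. Text against table at 12 patients.** More than 5% observed means 1 or more events; more than 10% means 2 or more (2/12 = 16.7%). The table says 3 or more for both. At a 20% adverse-event rate, P(X ≥ 2) = 0.725 and P(X ≥ 3) = 0.442.

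**The case against.** Four points carry weight.

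- **Delay more than loss.** Counts are cumulative, so a pending patient's event is counted at the next look. At a 20% rate the loss over all looks is only 1.6-2.6 points. This stands.
- **Pending is not the same as uninformative.** A reader might infer that recent patients have no chance of an event, or that 4-5 patients are missing from each look. The documents do not support that for adverse events: toxicity is assessed at every dosing visit, the 28-day extension belongs to phase I only, and 5 pending patients needs sustained accrual at the top of the range. For graft rejection the stricter reading is closer to the truth, because the calendar schedules no chimerism test before day 90-100.
- **No stated performance to fall short of.** A reader might also infer that the rule fails to deliver a promised hold probability. Section 9 states none. The 20% rate is an assumption made here; the text names 5% and 10%.
- **Other monitoring.** Under the Data Safety Monitoring Plan in Section 5, unexpected grade 3 and all grade 4-5 events go to the monitoring committee, grade 4-5 within 5 calendar days, and the committee can terminate the study. This mitigates only in part. That route does not cover an expected related grade 3 event, which the boundary does count. Routine review is twice a year, the same pace as 12 patients per six months, so it need not fall between looks.

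The text-table disagreement also has a larger effect at the first look than the pending patients do (0.725 against 0.442). That adds to the need for revision and does not remove this point.

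**Conclusion.** The point holds as a question of timing. The rule counts enrolled patients with no follow-up condition, and the table is reproduced by treating them all as fully observed. At about 2 per month, roughly 2-3 patients are partly observed at each look. At an assumed 20% related grade 3-4 rate, the first-look hold probability drops from 0.44 to about 0.29-0.34, or 0.26 if 3 patients contribute nothing. At 10% it drops from 0.11 to 0.05-0.07 when 2-3 contribute nothing. Over all looks at 20% it is about 0.92-0.94 instead of 0.95, with about 2-4 more patients enrolled before a hold.

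These figures rest on the assumed true rates, first dose at enrolment, the planned accrual, and event times spread evenly over 21 or 49 days. A longer gap between enrolment and first dose would increase the effect; slower accrual would reduce it. The documents do not support a claim that the trial lacks safety oversight or would fail to detect a high toxicity rate.

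**What to change.** Revise Section 9, Safety/Stopping Rules:

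1. Define the rows by the first 12, 24, 36, 48 and 51 patients.
2. State the adverse-event window that applies in phase II.
3. Run each look on schedule, but keep its row open until all its patients have completed that window and the day-100 chimerism assessment. A later event in those patients that reaches the boundary then triggers the hold at once, without waiting for the next look.
4. Report enrolled and evaluable counts at each look, and state the rule's hold probabilities under named true rates.
5. Reconcile the percentage thresholds in the text with the counts in the table.

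The cost is wording, tracking of evaluable status, and a slightly higher chance of a hold at the assumed 5% rate (about 6% instead of 4-4.5%). No look is postponed and no extra patients are needed. Postponing each look until its patients are evaluable would be a weaker remedy: a wait of 21-40 days at 2 per month lets in about 1.4-2.6 more patients (2 × 21/30.4 to 2 × 40/30.4), which gives back much of the gain.
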